5.5.2 Analysis supporting secondary objective(s)

5.5.2.1 Mixed Model for Repeated Measures (MMRM)

The first secondary endpoint (change in LDL-C) will be analyzed via a mixed model for repeated measures (MMRM) with an unstructured covariance matrix (representing the within-participants correlation). Study visit will be included as a repeated factor nested within participant:

$$\Delta LDL = treatment + CV\ risk\ category + scheduled\ visit + scheduled\ visit \\ * treatment + LDL_{baseline} + LDL_{baseline} * visit$$

with $LDL_{baseline}$ as the concentration of LDL-C at baseline.

The MMRM will also be used for the fourth secondary endpoint (change in SF-BPI) as described above with the only exception, that additional visits will be included into the model as per schedule of assessments, which leads to the following model:

$$\Delta SFBI = treatment + CV\ risk\ category + scheduled\ visit + scheduled\ visit \\ * treatment + SF_{BPI_{baseline}} + SF_{BPI_{baseline}} * visit.$$

The Kenward-Roger approximation will be used to estimate denominator degrees of freedom (Kenward and Roger, 1997).

If the model fails to converge with unstructured covariance matrix, either a compound symmetry (first choice) or first order autoregressive (AR1) (second choice) covariance structure will be applied.

In SAS the PROC MIXED procedure will be used. To fit the model, the REPEATED statement is used to specify the repeated measures factor, the unstructured covariance matrix will be specified using the TYPE eq UN optional parameter. Results will be presented with LSM and standard error (SE) for treatment effects. Any missing data are considered MAR (missing [conditionally] at random) and handled as such in the MMRM.

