2.6.2.1 Mean relative change in LDL-C

The null hypothesis to be rejected for the relevant secondary endpoint is:

- H_{02} : The mean relative changes from baseline in LDL-C level, averaged over all post baseline visits during the double-blind treatment period, are equal between treatment groups.

The relative change (percentage change) from baseline in LDL-C level averaged over the double-blind treatment period will be analyzed using a mixed model for repeated measures (MMRM) including treatment group, CV risk category, scheduled visit and the interaction of treatment group with scheduled visit as factors and baseline LDL-C level and the interaction of baseline LDL-C level with scheduled visit as covariates. To allow adjustment for correlations between time points within participants, an unstructured variance-covariance structure will be used. The null hypothesis of equal mean changes between both groups to the average over all post baseline visits will be tested by an appropriate linear contrast of the variable treatment and treatment by visit interaction.. The adjusted mean change from baseline as well as the treatment difference and their corresponding 95% confidence intervals will be presented.

Least square means of each treatment group and estimated treatment differences at visits and corresponding 95% confidence intervals will be tabulated and presented graphically.

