treatment group, CV risk category, scheduled visit and the interaction of treatment group with scheduled visit as factors and corresponding baseline SF-BPI score and the interaction of corresponding baseline SF-BPI score with scheduled visit as covariates. To allow adjustment for correlations between time points within participants, an unstructured variance-covariance structure will be used.

The null hypothesis of equal mean changes between both groups at day 360 visits will be tested by an appropriate linear contrast of the variable treatment and treatment by visit interaction. The adjusted mean change from baseline as well as the treatment difference and their corresponding 95% confidence intervals will be presented.

Least square means of each treatment group and estimated treatment differences at visits and corresponding 95% confidence intervals will be presented graphically.

Additionally, the odds ratio between inclisiran vs. placebo of the participants achieving a clinically relevant change in pain severity score and pain intensity score from baseline to Day 360 will be estimated using a logistic regression model. Treatment and CV risk category will be included as factors in the model. The odds ratio and its 95% confidence interval (CI) and p-value will be estimated.

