2.6.2.5 Control of Familywise type I error rate

1-sided p-values and alpha level of 0.025 are considered for the testing procedure.

[figure not shown]
Hypotheses are grouped into three families. The first family contains the primary hypothesis H_{01} . The second family contains two secondary hypotheses H_{02} and H_{03} . The third family contains the remaining secondary hypotheses H_{04} , H_{05} and H_{06} . A hierarchical testing strategy is applied to these three families to control the familywise type I error rate in the strong sense. First H_{01} is tested at level α . If it is rejected, we test the second family using a closed test at level α . If both hypotheses are rejected, we test the third family using the Hommel procedure at level α . When not all hypotheses in a family can be rejected, testing stops at the corresponding family and does not proceed to test the next family.

Within the second family, a closed test procedure based on weighted Simes tests is applied with 80% weight for H_{02} and 20% weight for H_{03} . First the two nominal p-values for the two hypotheses are simultaneously compared to α . If both nominal p-values are less or equal α , the two null hypotheses are rejected. Otherwise the individual nominal p-values will be compared to the pre-specified weighted alpha. If the p-value for H_{02} is less or equal 0.8α , H_{02} is rejected; if the p-value for H_{03} is less or equal 0.2α , H_{03} is rejected.

Within the third family, the Hommel procedure is applied. Let the ordered p-values for H_{04} , H_{05} and H_{06} be $p(1) \leq p(2) \leq p(3)$ and the corresponding hypotheses $H(1)$, $H(2)$ and $H(3)$. First if $p(3)$ is less or equal α , we can reject all three hypotheses. Otherwise, if $p(2)$ is less or equal $\alpha/2$, we can reject $H(2)$ and $H(1)$. Otherwise, if $p(1) \leq \alpha/3$ or ($p(1) \leq \alpha/2$ and $p(2) \leq 2\alpha/3$), $H(1)$ is rejected.

For more details see also [Figure 2-2](#).

Figure 2-2 Applied testing procedure

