3.1 Primary endpoint(s)

The assumption for the occurrence of LDL-C target attainment on day 90 in the inclisiran-arm is based on the ORION study data set. In CCI of participants achieved an LDL-C level CCI mg/dL target at day 90 CCI (Ray et al., 2020). In CCI of participants achieved an LDL-C level CCI mg/dL at day 90 CCI (Ray et al., 2020). Assuming CCI, approx. CCI of participants achieve their individual LDL-C target at day 90. For the assumption of LDL-C target attainment at day 90 in the placebo arm, the EXPLORER trial reports response rates for CCI (Ballantyne et al., 2007): CCI of participants achieved an LDL-C level CCI mg/dL at day CCI. Mean LDL-C level at day CCI was CCI, so it can be estimated that approx. CCI of participants may have reached the CCI target. Based on the study population and treatment regime herein, day CCI of EXPLORER trial likely relates to day 90 of the present study. With the above stated assumption of a CCI among the participant population, CCI of participants are considered to reach their LDL-C target at day 90. Considering the high LDL-C levels at baseline in the EXPLORER trial compared to ORION trials, herein, a slightly higher goal attainment rate of approx. CCI at day 90 for participants in the comparator arm is assumed. Under these assumptions, CCI participants per arm are required based on a chi-squared test of proportions to achieve 90% power on a two-sided, 5% significance level. In order to compensate for missing values and other protocol deviations, approximately 880 participants per arm (approximately 1760 participants in total) should be enrolled/randomized into this trial.

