4. For intercurrent event of double-blind treatment discontinuation, in case of missing RDO data and no occurrence of other intercurrent event such as PCSK-9 inhibitor impute missing values for participants in the inclisiran treatment groups using J2R.

Select all participants, impute missing values at scheduled post-baseline visits using the MI approach, under assumption of missing not at random (MNAR) that participants in inclisiran treatment groups will behave as participants treated with placebo, based on the fully conditional specification (FCS) method for 100 times and obtain 100 imputed datasets. Model will include same covariates as in step 1, except for treatment which is considered in the MNAR assumption.

This results in 100 imputed datasets.

5. Merge datasets from step 3 and step 4.

- a. For participants in inclisiran treatment groups discontinuing double-blind treatment prematurely take imputed values after discontinuation of double-blind treatment from step 4 if not after occurrence of other intercurrent event such as PCSK-9 inhibitor.
- b. For all other missing (including those for placebo participants) values take imputed values from step 3.

6. Derive endpoint variable for imputed values, e.g. change from baseline/response variable/percent change from baseline.

7. For each considered endpoint the specified analysis model will be applied on every of the 100 final multiply-imputed datasets where all missing values are filled (from MI or single imputation as defined by the respective strategy).

8. The results for the treatment effect from the 100 datasets will then be combined to obtain the statistical quantities of interest using Rubin's rule. Therefore, in SAS the PROC

MIANALYZE procedure is used and generates valid statistical inferences. If models failed to converge for a subset of imputations the remaining ones are used.

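### If the unstructured MMRM fails, the compound-symmetry fallback can move the Day 360 SF-BPI tests off 2.5% in either direction; only AR(1) can move the LDL-C test

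*SAP*

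**What the plan says.** The main analysis is sound. For the LDL-C endpoint (H02), SAP 2.6.2.1 states that "an unstructured variance-covariance structure will be used", and SAP 2.6.2.4 says the same for the SF-BPI scores (H05, H06). Protocol 12.5.2.1 and 12.5.2.4 name only the unstructured matrix.

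SAP 5.5.2.1 adds the contingency. On non-convergence, "either a compound symmetry (first choice) or first order autoregressive (AR1) (second choice) covariance structure will be applied". On inference it says "The Kenward-Roger approximation will be used to estimate denominator degrees of freedom". It names no sandwich estimator, no heterogeneous-variance structure and no structure based on elapsed days. That the fallback standard errors are model-based is inferred from this; the SAP does not say so in words.

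The contrasts differ. H02 tests the treatment difference averaged over all post-baseline visits. For H05 and H06, SAP 2.6.2.4 says: "The null hypothesis of equal mean changes between both groups at day 360 visits will be tested by an appropriate linear contrast". All are confirmatory: "1-sided p-values and alpha level of 0.025 are considered for the testing procedure" (SAP 2.6.2.5).

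SAP 5.5.3 steps 7 and 8 fit the model to 100 datasets with every missing value filled. Step 8 then gives its own rule for non-convergence: "If models failed to converge for a subset of imputations the remaining ones are used". The SAP does not say which of the two rules comes first.

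**The concern.** A fallback for a confirmatory test should keep its level whatever the unknown visit variances turn out to be. Compound symmetry and AR(1) each fit one common variance. A test at a single visit then borrows its standard error from the other visits. If Day 360 is more variable than the average visit, that standard error is too small and the test is anti-conservative; if it is less variable, the test is conservative.

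AR(1) has a second weakness. It counts visits and ignores days, but SAP Table 2-1 places the LDL-C analysis visits at Days 60, 90, 150, 330 and 360, with gaps of 30, 60, 180 and 30 days. It also makes correlation die away with visit number, which matters for an average over visits.

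The order of the two non-convergence rules matters too. One programmer could refit a failed imputation under compound symmetry while another discards it, so the pooled result for the same hypothesis could differ.

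**Working it through.** **Inputs from the documents.** One-sided alpha 0.025 (SAP 2.6.2.5), matching the two-sided 5% in SAP 3.1; about 880 per arm (SAP 3.1); SF-BPI visits at Days 30, 60, 90, 150, 210, 270, 330 and 360, and LDL-C visits as above (SAP Table 2-1). **Assumed:** all visit SDs and correlations, since neither document gives any.

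**The plan's own level.** 1 − Φ(1.960) = 0.025. Simulation with the unstructured matrix (880 per arm, complete data, 40,000 runs) gave 2.4–2.6% for both contrasts, so the main analysis holds its level.

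**H05/H06 under compound symmetry, complete data.** The fitted variance is the mean of the visit variances. With r = SD at Day 360 / √(mean visit variance), the actual one-sided error is Φ(−1.960/r).

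Rising paths: SD(t) = a + (b − a)·√((t − 30)/330). Falling paths: a straight line from Day 30 to Day 360.

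| SD, Day 30 to Day 360 | Mean variance | r | 1.960/r | Error |
|---|---|---|---|---|
| 1.4 to 1.8 | 2.719 | 1.092 | 1.795 | 3.6% |
| 1.2 to 1.8 | 2.490 | 1.141 | 1.718 | 4.3% |
| 1.0 to 1.8 | 2.281 | 1.192 | 1.644 | 5.0% |
| constant | – | 1.000 | 1.960 | 2.5% |
| 1.0 to 0.9 | 0.908 | 0.944 | 2.075 | 1.9% |
| 1.0 to 0.8 | 0.823 | 0.882 | 2.223 | 1.3% |

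Only r matters; r = 1.04 gives 3.0%. As a check, a straight-line 30% rise has r = 1.132 and formula value 4.2%, and simulation also gave 4.2%. AR(1) gives nearly the same Day 360 values.

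**H02 under compound symmetry, complete data.** The variance of an equally weighted mean of k visits is [v + (k − 1)c]/k, with v the mean variance and c the mean covariance. Compound symmetry estimates exactly these two quantities, so the error is 2.5% for any SD and correlation pattern (simulated 2.4%). If the model were instead fitted to incomplete data with 10–20% dropout, it would be 2.5–2.7%.

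**H02 under AR(1), five visits, equal SDs.** The model variance of the mean is [5 + 2(4ρ + 3ρ² + 2ρ³ + ρ⁴)]/25.

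- True correlation constant at 0.5: the fitted ρ is 0.5. Model variance is [5 + 2(2 + 0.75 + 0.25 + 0.0625)]/25 = 0.445; true variance is (1 + 4 × 0.5)/5 = 0.600. The SE ratio is √(0.445/0.600) = 0.861 and the error is Φ(−1.960 × 0.861) = 4.6%.
- Constant 0.4: SE ratio 0.853, error 4.7%. Constant 0.7: SE ratio 0.900, error 3.9%.
- Correlation decaying purely with elapsed time: 0.80 per 30 days gives 2.05%; 0.95 per 30 days gives 2.36%.
- Correlation that partly decays and partly persists: about 2.9–3.4%.

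**Not modelled:** the between-imputation variance that Rubin's rules add.

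**The case against.** The strongest objection is that the trigger is close to unreachable. The model is fitted to complete data on about 1,760 participants, with 5 × 6/2 = 15 covariance parameters for LDL-C and 8 × 9/2 = 36 for SF-BPI. Sparse late visits, a common cause of failure, do not arise. Iterated generalised least squares on 360 simulated complete datasets of 1,760 × 8 converged every time within 6 iterations. That is not PROC MIXED's algorithm, but it shows no ill-conditioning. This objection stands and sets the severity.

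Three stronger readings are tempting, and the documents do not support them.

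- A reader might infer that the whole fallback inflates H02. Compound symmetry does not, because SAP 5.5.3 completes the data. AR(1) comes into play only if a two-parameter compound-symmetry model fails as well.
- A reader might infer that both structures impose equal spacing. Compound symmetry ignores time; only AR(1) does this.
- A reader might infer that the direction is always inflation because change-from-baseline variability usually grows. Neither document gives visit SDs, so the conservative half of the range is equally open.

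The percentages are also per-test. H05 and H06 are reached only after H01, H02 and H03 are all rejected, and then through Hommel.

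On the two rules, it is fair to read SAP 5.5.2.1 as model-specific and step 8 as a general closing rule, so that the fallback comes first. That is the natural order, but it is not written down. This is an ambiguity rather than a contradiction.

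**Conclusion.** The point holds as a low-severity gap in a contingency rule. If the fallback is ever used, the level of H05 and H06 depends on an unknown ratio of visit SDs: about 3.6–5.0% for r of 1.09–1.19, and about 1.3–1.9% for SDs falling by 20% or 10%. H02 stays at 2.5% under compound symmetry. Under AR(1) it is about 3.9–4.7% with constant correlations of 0.4–0.7, and about 2.0–2.4% with purely time-decaying correlation. All SDs and correlations are assumptions. The planned unstructured analysis is not in question, and nothing here says that the trial's actual error rate is 3–5%. The unstated order between SAP 5.5.2.1 and step 8 of SAP 5.5.3 needs no assumed number.

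**What to change.** Reword the non-convergence rule in SAP 5.5.2.1 before database lock:

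1. Retry the unstructured fit, with other starting values or Fisher scoring.
2. If it still fails, use heterogeneous Toeplitz (TOEPH), then heterogeneous compound symmetry (CSH), in place of compound symmetry and AR(1).
3. With any structured matrix, use the sandwich (EMPIRICAL) standard error. On complete data a heterogeneous variance alone restores 2.5% for the Day 360 tests. The sandwich error is needed for the H02 average, because TOEPH still counts visits by lag and CSH does not in general reproduce the variance of the average.
4. Apply one structure per endpoint to all 100 imputed datasets.
5. State that this sequence comes before step 8 of SAP 5.5.3, which then covers only fits that still fail.

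The cost is wording only; no data or sample size changes. The Kenward-Roger correction is lost in the fallback, which is immaterial at about 880 per arm.

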5.5.2.2 Logistic regression

To analyze the number of muscle-related adverse events the same method as for the primary endpoint is used (see Section 5.5.1.1) with the adaptation that the model is given by:

$$\text{logit}(\#AE \geq 1) = treatment + CV\ risk\ category$$

5.5.2.3 Negative binomial model

The third secondary endpoint will be analyzed using a generalized linear model of the following form assuming a negative binomial distribution:

$$\#pain\ days = treatment + CV\ risk\ category + \log(time[y]).$$

In SAS the PROC GENMOD procedure is used with the DIST equal to NB statement to choose the negative binomial distribution and LINK equal to LOG as link function. The offset will be defined in the OFFSET option (eq LOGRISK).

If the model fails to converge a quasi-Poisson model will be fitted instead, with the exception of subgroup analyses.

5.5.2.4 Analysis of Covariance (ANCOVA)

The changes from baseline for different traits will be analyzed by an linear analysis of covariance of the following form:

$$\Delta \text{trait} = \text{treatment} + \text{trait}_{\text{baseline}} + \text{CV risk category}.$$

In SAS the PROC MIXED procedure will be used to run the different ANCOVAs. Results will be presented with LSM and standard error (SE) for treatment effects.

5.5.2.5 Time to event analysis

For the sensitivity analysis a Cox proportional hazards regression model will be applied in time-to-event analyses to test the null-hypothesis $H_0 = \frac{\lambda_{\text{inclisiran}}(t)}{\lambda_{\text{placebo}}(t)} = 1$, where $\lambda(t)$ is the hazard function for the event time of participants treated with Inclisiran and Placebo, respectively. The event time is thereby defined as the time to first experience of at least one muscle-related AE ((SMQ) rhabdomyolysis / myopathy). The Cox regression model will include terms for treatment and CV risk category.

The SAS procedure PROC PHREG will be used for analysis. Results will be presented with adjusted hazard ratios for treatment group comparisons and associated 95% confidence intervals. One-sided p-value from Z-test will be presented.

5.5.3 Multiple imputation

If not stated otherwise, imputation for primary and secondary analyses will be done by the following rules: For missing data, target day of the visit is considered to assess if missing is related or not related to intercurrent event. Absolute values are imputed corresponding endpoint variables are derived on imputed data.

Select data to fit the imputation model considering strategy applied for intercurrent events:

1. For primary endpoint all observed data will be included except for data collected after intercurrent events where composite strategy is applied, e.g. data collected after PCSK-9 inhibitors will be set to missing. Note, after death no data are collected, thus no need to take any action for while alive strategy. In case of occurrence of multiple intercurrent events e.g. double-blind treatment discontinuation and later PCSK-9 use, all data RDO data up to PCSK-9 inhibitor use will be used, others will be set to missing.
2. For secondary endpoints data all observed data will be included except for data collected after intercurrent events where hypothetical strategy is applied, these will be set to missing after intercurrent event. In case of occurrence of multiple intercurrent events e.g. double-blind treatment discontinuation and later PCSK-9 use, all RDO data up to

PCSK-9 inhibitor use will be used, others will be set to missing for LDL-C analyses where hypothetical strategy is applied for PCSK-9 inhibitor use.

3. Impute missing data using MAR (missing at random):

Select all participants, impute missing values at baseline and scheduled post-baseline visits, under assumption of missing at random (MAR), using the PROC MI procedure in SAS based on the fully conditional specification (FCS statement) method for 100 times and obtain 100 imputed datasets. Missing baseline values will be imputed using a model with treatment and CV risk category. Missing Day 30 values will be imputed using a model based on values of baseline, treatment and CV risk category. The same procedure will be repeated for subsequent visits.

This results in 100 imputed datasets.

For participants in the inclisiran treatment groups who discontinued double-blind treatment prematurely, set imputed values after discontinuation of double-blind treatment to missing, if not after occurrence of other intercurrent event such as PCSK-9 inhibitor, as these will be imputed using jump to reference (J2R) in step 4.

4. For intercurrent event of double-blind treatment discontinuation, in case of missing RDO data and no occurrence of other intercurrent event such as PCSK-9 inhibitor impute missing values for participants in the inclisiran treatment groups using J2R.

Select all participants, impute missing values at scheduled post-baseline visits using the MI approach, under assumption of missing not at random (MNAR) that participants in inclisiran treatment groups will behave as participants treated with placebo, based on the fully conditional specification (FCS) method for 100 times and obtain 100 imputed datasets. Model will include same covariates as in step 1, except for treatment which is considered in the MNAR assumption.

This results in 100 imputed datasets.

5. Merge datasets from step 3 and step 4.

- a. For participants in inclisiran treatment groups discontinuing double-blind treatment prematurely take imputed values after discontinuation of double-blind treatment from step 4 if not after occurrence of other intercurrent event such as PCSK-9 inhibitor.
- b. For all other missing (including those for placebo participants) values take imputed values from step 3.

6. Derive endpoint variable for imputed values, e.g. change from baseline/response variable/percent change from baseline.

7. For each considered endpoint the specified analysis model will be applied on every of the 100 final multiply-imputed datasets where all missing values are filled (from MI or single imputation as defined by the respective strategy).

8. The results for the treatment effect from the 100 datasets will then be combined to obtain the statistical quantities of interest using Rubin's rule. Therefore, in SAS the PROC

MIANALYZE procedure is used and generates valid statistical inferences. If models failed to converge for a subset of imputations the remaining ones are used.

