2.5.3 Handling of intercurrent events

The general strategy to account for different intercurrent events is summarized in [Table 2-2](#). Additional explanation is given in the following:

1. Discontinuation of investigational treatment:

Follow-up information after permanent discontinuation of investigational treatment, Retrieved Drop Out (RDO) data will be collected at regular study visits and will be included in the analysis, with treatments as assigned at randomization (treatment policy strategy). If no RDO data are collected missing data will be imputed using jump to reference as described in [Section 5.5.3](#).

2. Death:

For participants who die no subsequent LDL-C value can exist, therefore only pre-death data will be considered. For deceased participants the last value measured before death will be included into the analysis (while alive strategy).

3. Use of PCSK9 targeting non-study medication or lipid apheresis:

It could occur that participants are switched to PCSK9 targeting therapy after discontinuation of study medication or receive lipid apheresis. For the primary estimand participants who use PCSK9 targeting non-study medication or lipid apheresis will be considered as not achieving their LDL-C target (composite strategy).

4. COVID-19 pandemic impact on study:

For the primary estimand collected data will be included in the analysis. The treatment groups will be kept as assigned at randomization (treatment policy strategy). All observed data are used for the analyses, missing data are imputed as described in [Section 2.5.4](#).

Table 2-2 Account for different post randomization events for the primary endpoint reaching LDL-C target at day 90

Intercurrent event	Strategy
Permanent discontinuation of investigational treatment	Treatment policy strategy
Death	While alive strategy
Use of PCSK9- targeting non-study medication* or lipid apheresis	Composite strategy
COVID-19 pandemic impact on study	Treatment policy strategy
* evolocumab, alirocumab or commercially available inclisiran	

Change in background medication essentially concerns change in LLT during optimization. A change in background medication is therefore not considered as an intercurrent event because it is part of the treatments compared.

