2.5.4 Handling of missing values not related to intercurrent event

Missing values will be imputed by multiple imputation. In a first step the continuous LDL-C level will be imputed by $m = 100$ imputations based on FAS. From the imputed continuous LDL-C level the binary response variable will be derived against the individual LDL-C target and analyzed with the methods described in the related section. Results will be combined according to Rubin's rules on the log scale. The imputation model will impute missing values based on all observed values taking into account strategy applied for the respective intercurrent event. The imputation model will include randomized treatment arm and CV risk category. Details are described in [Section 5.5.3](#).

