2.6.3 Handling of intercurrent events

For the secondary estimand we consider the same intercurrent events as for the primary estimand (see [Section 2.5.3](#)). Except one specific exception described below, the proposed approach for all secondary endpoints for the intercurrent events of discontinuation of investigational treatment, the use of PCSK9 targeting non-study medication or lipid apheresis or the impact of the COVID-19 pandemic is the treatment policy strategy. For the intercurrent event of death a while alive strategy will be applied.

The first secondary endpoint of relative change (percentage change) from baseline to mean LDL-C level over the double-blind study period (averaged over all post baseline visits) will be handled differently for the use of PCSK9 targeting non-study medication or lipid apheresis. For this specific intercurrent event for this endpoint a hypothetical strategy will be applied.

If an assessment at a visit is affected by multiple intercurrent events, strategy for the intercurrent events occurring will be applied considering the following order of decreasing importance: first hypothetical, followed by while alive and treatment policy. For treatment policy, for the remaining missings PCSK-9 (MAR imputation) is considered over second treatment discontinuation (J2R imputation).

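### SAP 5.5.3 fills LDL-C and SF-BPI visits after death with imputed values (H02, H05, H06), against the while-alive strategy of SAP 2.6.3, and does not place the overwrite step for the primary endpoint

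*SAP*

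**What the plan says.** **Strategy for death.** For the secondary endpoints, SAP 2.6.3 says: "For the intercurrent event of death a while alive strategy will be applied". It gives no value or rule for carrying this out. For the primary endpoint, SAP 2.5.3 is specific: "For deceased participants the last value measured before death will be included into the analysis (while alive strategy". In the same section, users of PCSK9-targeting non-study medication or apheresis "will be considered as not achieving their LDL-C target (composite strategy".

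**Algorithm.** SAP 2.6.4 sends LDL-C change and both SF-BPI scores to SAP 5.5.3, which opens: "If not stated otherwise, imputation for primary and secondary analyses will be done by the following rules". Its parts bear on the point as follows.

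- Item 1 (primary endpoint) removes data collected after PCSK9 use from the model fit. It remarks that death needs no handling because nothing is collected afterwards. Item 2 (secondary endpoints) does not mention death.
- Step 3: "Select all participants, impute missing values at baseline and scheduled post-baseline visits, under assumption of missing at random (MAR".
- Step 4 applies jump to reference (J2R) to inclisiran participants who stopped treatment and have no later data, unless another intercurrent event has occurred.
- Step 5b: "For all other missing (including those for placebo participants) values take imputed values from step 3".
- Step 7 analyses 100 datasets with no missing values left. It allows the filling to come from multiple imputation or from a single value set by the intercurrent-event strategy.

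**Priority.** For the secondary endpoints, SAP 2.6.3 ranks hypothetical first, then while alive, then treatment policy.

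**The concern.** The remark in item 1 is true of collected data, but steps 3 to 5 create data. Once a visit after death is just another missing scheduled visit, it receives a value drawn as if the participant had lived. That answers what the score would have been without death, which is a hypothetical question. The stated one is what was seen while the participant was alive.

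H02, H05 and H06 are all in the confirmatory testing sequence, so the mismatch sits in pre-specified, alpha-controlled analyses. It also leaves programmers a choice. The J2R exemption for another intercurrent event names PCSK9 inhibitors as its example and does not say whether death counts. An inclisiran participant who stops treatment and then dies could therefore get J2R or missing-at-random (MAR) values.

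For the primary endpoint the outcome rules are clear, but no numbered step puts them into the imputed datasets.

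**Working it through.** **1. Tracing each endpoint through SAP 5.5.3**

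- *LDL-C and SF-BPI, death.* Item 2 takes no action. Step 3 covers all participants and all scheduled visits. Step 5a leaves out values after another intercurrent event, and 5b gives everything left over the MAR value. The single-value clause in step 7 cannot help, because no such value is defined for these endpoints. Result: visits after death are filled under MAR (or J2R, if death is not read as another intercurrent event). This conflicts with 2.6.3.
- *LDL-C, PCSK9 or apheresis use followed by death.* Hypothetical outranks while alive in 2.6.3, so imputation continues past death.
- *Primary endpoint, death or PCSK9/apheresis.* SAP 2.5.3 supplies the value (last value before death, or not achieved), and the step 7 clause lets it in. The step is missing; the rule is not.
- *Pain diary (H04).* Handled through the offset (SAP 2.6.4) and not imputed, so unaffected.

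**2. Size for the secondary endpoints**

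The documents state no death rate, so every rate and gap here is an assumption.

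- Participants affected, with 1776 randomised (Protocol, Amendment 3 rationale): 0.005 × 1776 = 8.9; 0.01 × 1776 = 17.8; 0.02 × 1776 = 35.5. That is about 9 to 36.
- Shift in an arm mean = d × g, where d is the fraction who die and g is the gap between the imputed and the while-alive value.
- SF-BPI at Day 360, g = 0.5 to 2 points: from 0.005 × 0.5 = 0.0025 to 0.02 × 2 = 0.04 points. SAP 2.6.2.4 takes 2 points as clinically relevant.
- LDL-C percent change, g = 10 to 50 percentage points, with all five central-laboratory visits (Days 60, 90, 150, 330, 360) imputed as the worst case: from 0.005 × 10 = 0.05 to 0.02 × 50 = 1.0 percentage point. If two of the five visits fall after death, the upper end is 1.0 × 2/5 = 0.4.
- If deaths and gaps are similar in the two arms, the between-arm difference moves less.

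**3. Size for the primary endpoint if the overwrite were left out**

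The planning response rates are redacted, so these inputs are also assumptions: p1 = 0.70 or 0.80 (inclisiran), p0 = 0.35 or 0.40 (placebo); PCSK9/apheresis use by Day 90 of q1 = 0.2% or 0.5% and q0 = 1% or 2%; f = 0.25 or 1, the success rate imputed to users as a fraction of the arm's rate.

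- With the rule: OR = odds(p1(1 − q1)) / odds(p0(1 − q0)).
- Without it: add f·p1·q1 and f·p0·q0 to the two proportions.
- Example, 0.80 vs 0.40, q = 0.2% vs 1%, f = 1. With the rule: (0.7984/0.2016) / (0.3960/0.6040) = 6.04. Without it: (0.80/0.20) / (0.40/0.60) = 6.00, a change of −0.7%.
- Lowest of all 32 combinations: 0.70 vs 0.40, 0.2% vs 2%, f = 1: 3.595 to 3.500, −2.6%.
- Highest: 0.80 vs 0.35, 0.5% vs 1%, f = 1: 7.359 to 7.429, +0.9%.

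The sign is not fixed. Taking f = 1 is generous, because step 3 conditions on earlier LDL-C and PCSK9 antibodies are the last drug step of the escalation scheme (Protocol 3.4).

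**The case against.** The best defence is that SAP 5.5.3 is only a default. SAP 2.5.3 says that only data from before death count, and 2.6.3 takes its intercurrent events from 2.5.3. The algorithm also sorts gaps by cause: "For missing data, target day of the visit is considered to assess if missing is related or not related to intercurrent event". A careful programmer would not keep values after death.

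For the primary endpoint this stands. A reader might infer that PCSK9/apheresis users are counted as successes in some of the 100 datasets, or that a deceased participant's Day 90 LDL-C is imputed. The documents do not support that. SAP 2.5.3 states both outcomes, the default wording of 5.5.3 yields to it, 2.5.4 limits imputation to gaps unrelated to intercurrent events, and step 7 admits strategy-defined values. What remains is an unplaced step.

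For the secondary endpoints it does not stand. SAP 2.6.3 refers to 2.5.3 for which events are considered, and the last-value rule there is written for LDL-C at Day 90. It does not say what while alive means for an average over visits or for a Day 360 pain score. No numbered step uses the sorting by cause to keep visits after death empty.

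Two other stronger readings also fail. A reader might infer that MAR values after PCSK9 or apheresis use contradict 2.6.3. That section has no composite rule: LDL-C gets a hypothetical strategy, which MAR implements, and SF-BPI gets treatment policy, with MAR named for what is still missing. A reader might also extend the point to all pain endpoints, but the diary is not imputed.

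**Conclusion.** The point holds for death in H02, H05 and H06: the written algorithm targets a different quantity from the stated estimand. For the primary endpoint it is a clarification of order, not a contradiction.

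The size is small. About 9 to 36 participants would be affected at an assumed 0.5% to 2% mortality, moving an arm's SF-BPI mean by at most 0.04 points and its LDL-C change by at most 1 percentage point. If the primary overwrite were omitted, the odds ratio would move by −2.6% to +0.9% under the assumed inputs. No decision is expected to change. All of this rests on assumed rates, since the documents give no figures for deaths or PCSK9/apheresis use. The case for acting is that confirmatory analyses should estimate what they declare, and the repair is cheap.

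**What to change.** Amend SAP 5.5.3 and 2.6.3:

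1. Do not carry forward from steps 3 to 5 any value for a visit whose target day is after the date of death. State that death is handled by neither MAR nor J2R.
2. Define while alive for the secondary endpoints in the spirit of 2.5.3: the last value before death for SF-BPI at Day 360, and the average of visits up to death for LDL-C. Filling each LDL-C visit after death with the participant's own mean m over the k visits before death achieves this, since (k·m + (5 − k)·m)/5 = m. Say what is used when there is no post-baseline value.
3. In 2.6.3, rank while alive above hypothetical for visits after death.
4. After step 6, state that in all 100 datasets primary-endpoint participants who meet the PCSK9/apheresis rule of 2.5.3 are set to not achieved, and those who died before Day 90 take their last LDL-C before death.

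Leaving visits after death blank in the MMRM would not be enough. SAP 5.5.2.1 treats missing data in that model as MAR, so it would give the same hypothetical estimate implicitly.

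The cost is a few sentences and a few lines of code, with no new data and no burden on participants.
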